2.1.4.2 Deaths

The deaths observation periods are per the observation periods defined in [Section 2.1.4](#).

- Death on-treatment: deaths occurring during the on-treatment period.
- Death post-treatment: deaths occurring during the post-treatment period.

2.1.4.3 Laboratory safety variables

Clinical laboratory data consists of blood and urine analysis, including hematology, biochemistry, and urinalysis. Clinical laboratory values will be converted into standard international units and these international units will be used in all listings and tables.

The laboratory parameters will be classified as follows:

- Hematology
 - **Red blood cells, platelets, and white blood cells:** hemoglobin, hematocrit, red blood cell count, white blood cell with differential, and platelet count,
 - **Coagulation:** prothrombin time (expressed as international normalized ratio [INR]), activated partial thromboplastin time (aPTT).
- Biochemistry
 - **Metabolism:** fasting glucose, total protein, albumin,
 - **Electrolytes:** sodium, potassium, chloride, bicarbonate/carbon dioxide, calcium, corrected calcium (formula included in [Section 2.5.1](#)), magnesium, phosphate,

- **Renal function:** uric acid, creatinine, creatinine clearance (eGFR), urea or blood urea nitrogen (BUN),
- **Liver parameters:** aspartate aminotransferase (AST), alanine aminotransferase (ALT), bilirubin (total and direct), alkaline phosphatase, LDH,
- **Hormonal:** thyroid stimulating hormone (TSH), and free T4.
- Urinalysis
 - Qualitative analyses (dipstick),
 - Quantitative analyses: sodium, potassium, calcium, chloride, red blood cell, leukocytes, protein, glucose, ketone, pH, bilirubin, nitrate, and specific gravity.

Technical formulas are described in [Section 2.5.1](#).

2.1.4.4 Vital signs variables

Vital signs include: systolic and diastolic blood pressure, heart rate, temperature, respiratory rate, and weight.

2.1.4.5 R code for conditional power and stopping boundary calculation Electrocardiogram variables

Twelve-lead ECG will be performed at screening and as clinically indicated.

2.1.4.6 Other safety endpoints

Other safety endpoints include:

- Chest X-ray at screening and as clinically indicated.
- Cytokines (TNF- α , IL-1- β , IL-6, IFN- γ), markers of complement (C3a, C4, CH50), serum tryptase.
- Indirect antiglobuline test (IAT).

2.1.5 Immunogenicity variables

Anti-drug antibodies (ADA) against isatuximab and cemiplimab were collected according to the PK/PD flowcharts of the protocol.

Observation period

The observation period will be defined for isatuximab and cemiplimab separately, which are divided into 2 periods: ADA pre-treatment and ADA on-study observation.

- ADA pre-treatment period: The ADA pre-treatment period is defined as the date from signed informed consent to the date and time of first study drug administration.
- ADA on-study observation period: the ADA on-study observation period is defined as the date and time from the first study drug administration until the end of the study.

ADA attributes

Pre-existing ADA is defined as ADA that are present in samples drawn during the pre-treatment period.

Treatment boosted ADA is defined as pre-existing ADA with a significant increase in the ADA titer during the study compared to the baseline titer. A low serial dilution schema (2-fold or 3-fold) should be applied during titration. A difference in titer values of two titer steps between treatment or follow-up sample and its baseline sample is considered significant. For examples, at least a 4-fold increase in titers for 2-fold serial dilution schema (or 9-fold increase in titers for 3-fold serial dilution schema). If no titer could be determined for a positive sample, the titer will be reported as the minimal required dilution of the assay.

Treatment-induced ADA is defined as ADA that developed at any time during the ADA on-study observation period in patients without pre-existing ADA (including patients without pretreatment samples). If the baseline ADA sample is missing or non-reportable and at least one reportable ADA sample is available during the treatment (including follow-up period) the baseline sample will be considered as “negative” for data analysis. This is considered being a conservative approach for ADA assessment.

Subject status

Among evaluable population for immunogenicity (described in [Section 2.3.5](#)), following patient status will be defined:

- ADA-positive subject: A subject with at least one treatment induced or treatment boosted ADA-positive sample at any time following the first study treatment administration.
- ADA-negative subject: Subject without any treatment induced or treatment boosted ADA-positive sample during the on-study observation period.
- ADA-inconclusive subject: A subject who cannot irrefutably be classified as ADA-negative (eg, all post baseline samples inconclusive).

Overview of the ADA response

Two main categories can be reported for the epidemiology of an ADA immune response: ADA prevalence and ADA incidence:

- ADA prevalence is defined as the proportion of all patients tested positive for ADAs (including preexisting antibodies, treatment boosted ADAs and treatment induced ADAs) at any point.
- ADA incidence is defined as the proportion of subjects found to either have seroconverted (treatment induced ADAs) or boosted their pre-existing ADA response during the on-study observation period. Only evaluable subjects (described in [Section 2.3.5](#)) are considered for computing ADA incidence.

Kinetics of the immune response

- **Onset of ADA:** refers to the time period between the initial drug administration and the first instance of treatment induced ADAs (in days). The “median time to ADA development” and the quartiles Q1 and Q3 will be reported.
- **Duration of ADA:** ADA duration will be calculated as the date of last treatment induced.
 - ADA sample minus date of first treatment induced or treatment boosted ADA sample + 1.
- ADA duration will be calculated only for patients with at least two ADA positive samples. Median duration of an induced ADA response and the quartiles Q1 and Q3 should be reported.
- **Transient ADA response** is defined by:
 - Treatment induced ADA detected only at one sampling time point during the ADA on study observation period (excluding the last sampling time point), OR
 - Treatment induced ADA detected at two or more sampling time points during the treatment (including follow-up period if any), where the first and last ADA-positive samples (irrespective of any negative samples in between) are separated by a period less than 16 weeks, and the patient’s last sampling time point is ADA negative.
- **Persistent ADA response** is defined by:
 - Treatment induced ADA detected at two or more sampling time points during the ADA on-study observation period, where the first and last ADA-positive samples are separated by at least 16 weeks (irrespective of any negative samples in between).
- **Indeterminate ADA** is defined by:
 - Treatment induced ADA detected only at the last sampling time point, OR
 - The last two samples being ADA-positive and separated by a period of less than 16 weeks.

Treatment-boosted ADAs are excluded from the analysis of ADA kinetics.

2.1.6 Pharmacokinetic variables

The PK sampling times for isatuximab and cemiplimab were provided in the PK/PD flowcharts of the protocol.

The following PK parameters (listed in [Table 5](#)) will be calculated with pharmacokinetic data management system (PKDMS) software (Pharsight) V3.0; using non-compartmental analysis (NCA) from isatuximab and cemiplimab concentrations after the first administration on Cycle 1. The parameters will include, but may not be limited to the following:

Table 5 - List of pharmacokinetic parameters and definitions after the first administration

Parameters	Analyte		Definition
	Cemiplimab	Isatuximab	
C_{eoi}	•	•	Concentration observed at the end of intravenous (IV) infusion
C_{max}	•	•	Maximum concentration observed
t_{max}	•	•	Time to reach C_{max}
C_{last}	•	•	Last concentration observed above the lower limit of quantitation
t_{last}	•	•	Time of C_{last}
AUC_{0-14d} or AUC_{0-28d}	•		Area under the concentration versus time curve calculated using the trapezoidal method over the dosing interval (DL1=14 days and DL-1=28 days)
AUC_{0-7d}		•	Area under the plasma concentration versus time curve calculated using the trapezoidal method over the dosing interval (7 days)

C_{trough} are defined as sample collected just before treatment administration during repeated dosing.

In addition, Populations PK approaches may be used for both compounds and PK estimates may be used to conduct exploratory exposure-response analyses for safety and efficacy and PK/PD analyses for relevant biomarkers. If done, the data generated will be reported in stand-alone report(s).

2.1.7 Biomarker endpoints

2.1.7.1 Immune Genetic Determinants

Germline genetic data of Fc gamma receptor (FCGR), human leukocyte antigen (HLA) and killer-cell immunoglobulin-like receptor (KIR) genes will be analyzed on blood samples collected on Day 1 of Cycle 1:

- FCGR polymorphisms (FCGR2A and FCGR3A): For each gene, the results will be of the form AA, Aa or aa with A and a-alleles, the major and minor allele, respectively.
- HLA genotypes: HLA-A, HLA-B and HLA-C have been typed for each gene. The results will be epitope genotypes (Table 6) and allele genotypes.

Table 6 - Epitopes of HLA Class I recognized by KIR

HLA class I	Epitope	Amino-acid at position ^a					Associated allotypes
		77	80	81	82	83	
HLA-B	Bw6	Ser	Asn	Leu	Arg	Gly	
	Bw4	Asn	Thr	Ala	Leu	Arg	
	Bw4	Asn	Ile	Ala	Leu	Arg	
	Bw4	Asp	Thr	Leu	Leu	Arg	
	Bw4	Ser	Thr	Leu	Leu	Arg	
	Bw4	Ser	Thr	Ala	Leu	Arg	
HLA class I	Epitope	77	80	81	82	83	
HLA-A	Aw4	Asn	Ile	Ala	Leu	Arg	A*23; A*24
	Aw4	Ser	Ile	Ala	Leu	Arg	A*32
	A3	Key residues not yet published					A*03
	A11	Key residues not yet published					A*11
HLA class I	Epitope	77	80				
HLA-C	C1	Ser	Asn				
	C2	Asn	Lys				

^a Numbering from the first codon of the mature protein

- KIR genotypes: The presence or absence of 16 KIR genes will be screened. A KIR gene will be defined as present if at least one assay gives positive results; otherwise it will be defined as negative.

2.1.7.2 Immune phenotyping

Immune phenotyping in bone marrow (baseline, D1 of Cycle 3) and/or peripheral blood (baseline, D1 of Cycle 3 and EOT) will be assessed. The blast cells and immune cell populations include MDSC cell, B-cell, T-cell and NK-cell subsets and regulatory T cells (Treg)/CD8 effector ratio will be determined by multiparametric flow cytometry based on the expression of different cell surface markers.

2.1.7.3 Adaptive immune response

Adaptive immune response (TCR repertoire profiling) will be assessed in blood and bone marrow samples, which are collected at screening, D1 of Cycle 3 (blood only) and at CR.

Adaptive immune response (humoral and cellular immune responses to myeloma-related tumor antigens) will be assessed in blood prior to pre-medication and IMP administration on D1 of Cycle 1, Cycle 2, Cycle 4, Cycle 7 and Cycle 10 and in disease progression patients at EOT. Humoral response will be assessed in all sites. Cellular response will be assessed in patients at selected sites.

2.1.7.4 PD1-PDL1 expression

PD1-PDL1 expression will be assessed using archival bone marrow biopsy.

2.1.7.5 Blood typing interference test

Blood typing interference test will be done on blood sample.

2.1.8 Health related quality-of-life (HRQL) endpoints

Not applicable following Protocol Amendment 3.

2.1.9 Health economic endpoints

Not applicable.

2.1.10 Further therapy after discontinuation of investigational medicinal product administration during the study

Further therapies after discontinuation of study treatment will be collected on a specific eCRF page. The following information will be collected: relapse/progression date, best response, drug/medication (brand or generic name), start date and end date (if available)/ongoing (otherwise).

2.2 DISPOSITION OF PATIENTS

This section describes patient disposition for both patient study status and the patient analysis populations. Disposition will be described separately for Phase 1 and Phase 2 patients, based on the analysis population defined in [Section 2.3](#).

Screened patients are defined as any patients who signed the informed consent. Randomized patients and all treated/safety patients are defined in [Section 2.3](#).

For patient study status, patients in each of the following categories will be provided in a summary table or a flowchart diagram:

- Screened patients.
- Screen failure patients and reasons for screen failure (if any).
- Randomized patients (Phase 2 only).
- Randomized but not treated patients (Phase 2 only).
- Randomized and treated patients (Phase 2)/treated (Phase 1).
- Patients who discontinued study treatment.
- Patients still on treatment.
- Status at last study contact.

A summary of the reasons for definitive and premature treatment discontinuation for any compound by arm will be provided. Definitive treatment discontinuation is defined as the discontinuation of all the study drugs. Premature treatment discontinuation (only for the combination arms) is defined as the discontinuation of at least one of the study drugs but at least one is continued. Listing of the reasons for treatment discontinuation at time of the analysis will be provided.

Patients in each country and center will be summarized using the randomized population.

All critical or major deviations potentially impacting efficacy analyses, randomization, and drug-dispensing irregularities and other major or critical deviations will be summarized in tables giving numbers and percentages of deviations by arm.

Additionally, the following analysis populations will be summarized:

- ITT/randomized population.
- Safety population.
- Pharmacokinetics population.
- ADA evaluable population.

Definition of study populations are provided in [Section 2.3](#).

2.2.1 Randomization and drug dispensing irregularities

For the Phase 2, randomization and drug-dispensing irregularities occur whenever:

- A randomization is not in accordance with the protocol-defined randomization method, such as a) an ineligible patient is randomized, b) a patient is randomized twice. OR,
- A patient is dispensed an IMP not allocated by the protocol-defined randomization, such as a) a patient at any time in the study is dispensed a different treatment IMP than as randomized (which may or may not contain the correct-as-randomized IMP), or b) a non-randomized patient is treated with IMP reserved for randomized patients.

All randomization and drug-dispensing irregularities will be documented in the clinical study report. The irregularities will be categorized and summarized among randomized patients (number and percentages). Non randomized and treated patients in Phase 2 (if any) will be described separately.

Randomization and drug-dispensing irregularities to be prospectively identified include but are not limited to:

- Study treatment administration without IRT transaction.
- Patient randomized twice.
- Treatment taken or schedule different from randomized treatment/schedule.

2.3 ANALYSIS POPULATIONS

Unless otherwise specified, analysis population will be defined separately for Phase 1 and Phase 2 patients.

2.3.1 Intent to treat (ITT)/Randomized population (Phase 2 only)

The intent to treat/randomized population includes all patients from Phase 2 who gave their informed consent and were assigned a randomization number by the IRT, regardless of whether the patient was treated or not. In this population, patients will be analyzed according to the arm allocated by IRT, regardless of whether patients received any study drug or receive a different study drug from which they were randomized.

For any patient randomized more than once, only the data associated with the first randomization will be used for analysis.

This population is the primary population for all efficacy analyses.

2.3.2 All treated (AT)/safety population

The all treated/safety population is defined by phases.

For Phase 1, the all treated/safety population is defined as all screened patients who received at least one dose or a part of a dose of the study treatments (isatuximab or cemiplimab), regardless of the amount of treatment administered.

For Phase 2, the all treated/safety population is defined as all randomized patients who received at least one dose or a part of a dose of the study treatments (isatuximab or cemiplimab), regardless of the amount of treatment administered.

- Patients who receive at least 1 cemiplimab dose (even incomplete) during the trial will be analyzed in the combination arms:
 - Patient who receive at least 1 cemiplimab dose at Day 15 of any cycle will be analyzed in Q2W arm. Patient without any cemiplimab dose at Day 15 of any cycle will be analyzed in Q4W arm.
- Patients who receive isatuximab only throughout the trial will be analyzed in isatuximab control arm.

Randomized patients from whom it is unclear whether they took the IMP will be included in the safety population, and included in the treatment arms as randomized.

Non-randomized but treated patients will not be part of the safety population; however, their safety data will be presented separately.

This population is the primary population for the analysis of all exposure and safety parameters (except for DLT evaluation). Phase 1 and Phase 2 patients will be analyzed separately.

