Cemiplimab has been generally well tolerated, and the reported AEs have been similar to what have been observed with other PD-1 inhibitors. In study 1423, the most common treatment-emergent adverse events (TEAEs) occurring in 10% or more of patients were fatigue, nausea, decreased appetite, anemia, constipation, arthralgia, diarrhea, dyspnea, cough, pyrexia, vomiting, asthenia, and back pain. No protocol-defined dose limiting toxicities have been observed. Potential immune-related TEAEs (irTEAEs) have been observed in 33.7% patients including Grade 3 or higher in 8.2% patients. Treatment-related irTEAE occurring in more than 1% of patients included arthralgia (8.2%), diarrhea (6.5%), pruritus (4.5%), hypothyroidism (4.2%), rash maculo-papular (3.7%), AST increased (3.4%), rash (2.8%), ALT increased (2.5%), pneumonitis (2.3%), rash pruritic (1.7%), stomatitis (1.7%), hyperthyroidism (1.1%) 5.1% patients experienced serious irTEAE. Events of Grade 3 or higher occurring in more than 1 patient included: AST increase (n=3, 0.8%), pneumonitis (n=3, 0.8%), ALT increased (n=2, 0.6%) and diabetic ketoacidosis (n=2, 0.6%). Events occurring in 1 patients (0.3%) included: arthralgia, autoimmune hepatitis, colitis, hepatic failure, hyperbilirubinaemia, hyperthyroidism, paraneoplastic encephalomyelitis, transaminases increased. the events of paraneoplastic encephalomyelitis and hepatic failure were with fatal outcome. Five patients (1.4%) experienced a total of 8 cemiplimab-related infusion-related reactions (IRRs), all were non-serious and Grade 2 except 1 Grade 1 event. One patient treated at 10 mg/kg monotherapy in Study 1423 with soft tissue sarcoma died because of anti-HuD paraneoplastic encephalomyelitis; 16 other patients died due to progression of disease.

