6.5.5 General guidelines for the management of IARs

See [Appendix H](#).

Patients should routinely receive premedications prior to isatuximab infusion as detailed in [Section 8.2](#) to reduce the risk and severity of IARs commonly observed with mAbs.

Infusion associated reactions (which include NCI-CTCAE, version 4.03 terms "allergic/hypersensitivity reactions" and "cytokine release syndrome/acute infusion reaction") typically occurs within 24 hours from the start of the infusion. If an IAR is observed, patients must also be informed of the potential risk of recurrent allergic reactions at subsequent infusions.

Summary of IAR management is provided in [Table 5](#).

Patients who experience Grade 2 IARs may resume cemiplimab/isatuximab infusion after temporary interruption, under close monitoring and with therapy as needed. Patients may receive additional medication per the judgment of the Investigator. Additional recommended medications

are: diphenhydramine 25 mg IV (or equivalent) and methylprednisolone 100 mg IV (or equivalent).

Once a Grade 2 IAR has improved or resolved to Grade ≤ 1 , the infusion may be restarted:

- For cemiplimab, the infusion should be restarted at one half the original infusion rate.
- For isatuximab, the infusion should be restarted at one half the original infusion rate, see [Section 8.4](#) for infusion rate. If symptoms do not recur after 30 minutes, the infusion rate may be increased in 50 mg/hour increments every 30 minutes, to a maximum of 400 mg/hour. Patients with Grade 3 or 4 IAR must have cemiplimab and/or isatuximab permanently discontinued and appropriate therapy should be administered:

If a Grade 3 or high IAR occurred during cemiplimab infusion, cemiplimab should be permanently discontinued. Patient can continue treatment with isatuximab.

If a Grade 3 or high IAR occurred after the start of isatuximab infusion, patient should be permanently discontinued the treatment of both cemiplimab and isatuximab.

Should an IAR of Grade ≥ 2 occur, additional blood sampling during the AE is required for analysis of cytokine levels (TNF- α , IL-6, IL-1- β , and IFN- γ), markers of complement activation (C3a, C4, CH50), serum tryptase, and markers of potential TLS (uric acid, lactate dehydrogenase [LDH], BUN/creatinine, potassium, phosphate, corrected calcium or ionized calcium). The infusion reaction and the therapy administered must be documented in the CRF.

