Grade 2 or higher IARs must be reported as AESIs (see [Section 10.5](#)). Study personnel should consult the Medical Monitor for further guidance regarding re-treatment of patients with infusion reactions and regarding issues of premedication management (eg, alternative medications for patients allergic or intolerant to premedication agents) or to determine if locally used equivalent medications are acceptable.

Table 5 - IAR management

Infusion Related Reaction grading (NCI-CTCAE v4.03 criteria)	Recommendation

Mild Grade 1 Infusion interruption or intervention not indicated
	
Continuation of cemiplimab/ isatuximab infusion is per the judgment of the Investigator following close direct monitoring of the patient's clinical status. Cemiplimab/Isatuximab infusion may be stopped at any time if deemed necessary. If stopped, IAR will be classified as Grade 2 as per NCI-CTCAE definition.

Moderate Grade 2 Therapy or infusion interruption indicated but responds promptly to symptomatic treatment (eg, antihistamines, NSAIDS, narcotics, IV fluids); prophylactic medications indicated for ≤ 24 hrs)
	
Stop cemiplimab/isatuximab infusion. Give additional medication(s) with IV diphenhydramine 25 mg IV (or equivalent) and/ or IV methylprednisolone 100 mg (or equivalent) as needed. cemiplimab*/Isatuximab** may be resumed only after patient recovery, with close monitoring.
 
Blood samples for safety labs must be collected at listed as below: Important: additional blood sampling during the AE is required for analysis of cytokine levels (TNF-α, IL-6, IL-1-β, and IFN-γ), markers of complement activation (C3a, C4, CH50), serum tryptase, and markers of potential TLS

Infusion Related Reaction grading (NCI-CTCAE v4.03 criteria)	Recommendation

Severe or Life-threatening Grade 3: Prolonged (eg, not rapidly responsive to symptomatic medication and/or brief interruption of infusion); recurrence of symptoms following initial improvement; hospitalization indicated for clinical sequelae
	
Stop cemiplimab/isatuximab infusion. Give additional medication(s) with diphenhydramine 25 mg IV (or equivalent) and/ or IV methylprednisolone 100 mg (or equivalent) and/or epinephrine as needed. If IAR occurred during cemiplimab infusion, permanently discontinue cemiplimab. Continue treatment with isatuximab. If IAR occurred after the start of isatuximab infusion, permanently discontinue both cemiplimab and isatuximab.

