8.3 DOSING REGIMEN AND SEQUENCE

8.3.1 Dosing regimen

Isatuximab:

- For isatuximab alone as control, and at DL1 and DL-1: 10 mg/kg QW for 4 weeks followed by Q2W (ie, on Days 1, 8, 15 and 22 in Cycle 1, and on Days 1 and 15 in Cycle 2 and beyond, of a 28-day cycle).
- For DL-2: 10 mg/kg Q2W (ie, on Days 1 and 15 every cycle, of a 28-day cycle).

Cemiplimab:

- For DL1: 250 mg Q2W (ie, on Days 1 and 15 in all cycles of a 28-day cycle).
- For DL-1 and DL-2: 250 mg Q4W (ie, on Day 1 in all cycles of a 28-day cycle).

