2.1.3.1 Primary efficacy endpoint (Phase 2 only)

The primary efficacy endpoint is ORR, defined as the proportion of patients with CR (including sCR), VGPR or PR as BOR as assessed by the investigator. BOR will be derived using disease assessments (overall response CRF page) from the start of treatment through the entire study excluding any assessments performed after disease progression (that is confirmed), the cutoff date or following the start of further therapies for MM (see Figure 1). The ordering of evaluations from best to worse is: sCR, CR, VGPR, PR, MR, stable disease (SD), progressive disease (PD), not evaluable (NE). BOR for patients without response assessment will be 'Not evaluable'. BOR will be the best sequential response based on the investigator's disease assessments as determined by the criteria in Table 3. In addition, the following rules will be applied:

- BOR will be NE for patients who received at most 2 isatuximab administrations with investigator assessment of response of SD or better at Cycle 1 or end of treatment.
- BOR will be PD for patients without response assessment who received 1 cycle of treatment and died due to PD or had symptomatic deterioration within 30 days of last study treatment administration.

Symptomatic deterioration will not be considered as progression in the primary analysis of ORR.

Table 3 - Sequential response determination for investigator response assessment

Overall response at Cycle n	Overall response at Cycle n+1 ^a	Sequential response
sCR	sCR	sCR
CR	sCR	CR
sCR	CR	CR
CR	CR	CR
sCR/CR	VGPR	VGPR ^b
sCR/CR	PR	PR
VGPR	sCR/CR/VGPR	VGPR ^b
VGPR	PR	PR

Overall response at Cycle n	Overall response at Cycle n+1 ^a	Sequential response
PR	sCR/CR/VGPR/CR/PR	PR
sCR/CR/VGPR/PR	NE/No further evaluation/SD/PD	MR ^c
MR	Any	MR
Any	MR	MR
NE/SD/PD	sCR/CR/VGPR/PR	MR ^c
NE/PD/SD	SD	SD
SD	No further evaluation/NE/PD	SD
NE	SD	SD
PD	No further evaluation/NE	unPD ^e
PD	PD	PD
NE	PD	unPD ^e
NE	No further evaluation	NE
No evaluation ^d		PD ^d

a Disease assessment are planned to be performed every cycle. Disease assessment performed after the start of new anticancer treatment will be excluded from the derivation of BOR.

b Sequence provided for programming purpose.

[figure not shown]
c Unconfirmed PR or CR will be considered MR.

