SOC and PT	
 Primary SOC: internationally agreed order PT: decreasing order of frequency of Isa + CemQ2W arm 	
By treatment arms (and all patients if Phase 1): n (%) of patients with any event and n (%) of patients with event of Grade ≥3
	
 All TEAEs TEAEs occurring in ≥5% of the patients (in any group for Phase 2) Drug-related TEAEs Serious TEAEs Drug related serious TEAEs TEAEs leading to isatuximab discontinuation TEAEs leading to cemiplimab discontinuation TEAEs leading to dose interruption of isatuximab TEAEs leading to dose interruption of cemiplimab TEAEs leading to dose delay of isatuximab TEAEs leading to dose delay of cemiplimab TEAEs leading to dose reduction^a of isatuximab TEAEs leading to dose reduction^a of cemiplimab Pre-treatment AEs; Serious pre-treatment AEs Post-treatment AEs; Serious post-treatment AEs

MedDRA variables	Sorting	Layout	Events
SOC and PT	
 Primary SOC: internationally agreed order PT: decreasing order of frequency of Isa + CemQ2W arm 	
By treatment arms (and all patients if Phase 1): n (%) of patients with any event and n (%) of patients with event of Grade ≥ 3
	
IR analysis:
 
 IR diagnosis (as reported by investigator) Symptoms of IR (as reported by investigator) TEAEs (related; regardless of relationship) within 24 hours from the start of each infusion TEAEs (related; regardless of relationship) from the selected CMQ within 24 hours from the start of each infusion TEAEs (related; regardless of relationship) from the selected CMQ (not limited to those occurring within 24 hours from the start of each isatuximab infusion)
SOC and PT	
 Primary SOC: internationally agreed order PT: decreasing order of frequency of Isa + CemQ2W arm 	
By treatment arms (and all patients if Phase 1): n (%) of patients with any event and n (%) of patients with event of Grade ≥ 3
	
irAE analysis:
 
 irAE reported as AESI by investigator AEs as defined by irAE selected grouping of AEs occurring during the treatment emergent and extended safety follow up periods (related to cemiplimab; regardless of relationship) AEs occurring during the treatment emergent and extended safety follow up periods (related to cemiplimab; regardless of relationship)

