2.4.5.3 Deaths

Number (%) of patients who died by study period (on-treatment and post-treatment, within 60 days from first dose of study treatment), and cause of death will be summarized. A listing of patients who died while participating in the study including cause of death, death date, days from first and last dose to death, preferred term, and causal relationship to isatuximab/cemiplimab (when applicable) will be provided.

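### SAP 2.3.2 counts Q2W-allocated patients who die or stop cemiplimab before any Day 15 dose under Q4W, so the Q2W safety column cannot show those events

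*SAP*

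**What the plan says.** Protocol 13.3.1 asks for an as-treated safety population and gives no rule for telling the two combination schedules apart. SAP 2.3.2 supplies one. Anyone with at least one cemiplimab dose, even incomplete, goes to a combination arm; anyone with a Day 15 dose in any cycle goes to Q2W; and "Patient without any cemiplimab dose at Day 15 of any cycle will be analyzed in Q4W arm". The randomised arm is used only when it is unclear whether the patient took study drug, which does not cover a known Day 1 dose. The Day 15 test is not among the changes to the protocol listed in SAP 1.5.

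Protocol 8.3.1 sets the Q2W schedule as "For DL1: 250 mg Q2W (ie, on Days 1 and 15 in all cycles of a 28-day cycle"; Q4W is Day 1 only.

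SAP 2.4.5 runs all safety analyses on this population. Two outputs matter most here. One is the death summary in SAP 2.4.5.3: "Number (%) of patients who died by study period (on-treatment and post-treatment, within 60 days from first dose of study treatment". The other is the set of discontinuation tables in SAP 2.4.5.2 (Table 7), including "TEAEs leading to cemiplimab discontinuation".

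Protocol 6.5.5 documents routes to a stop before Day 15. Where a Grade 3 or higher infusion reaction "occurred after the start of isatuximab infusion, patient should be permanently discontinued the treatment of both cemiplimab and isatuximab", both drugs end, and isatuximab is given on Days 1 and 8 of Cycle 1. For a reaction of that grade during the cemiplimab infusion, Table 5 says: "If IAR occurred during cemiplimab infusion, permanently discontinue cemiplimab. Continue treatment with isatuximab". Death, progression and withdrawal are further routes.

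**The concern.** Membership of the Q2W safety column depends on something that happens after randomisation and that toxicity can prevent. A Q2W-allocated patient whose treatment ends before the first Day 15 dose has received nothing inconsistent with Q2W, yet the patient and the event are reported under Q4W. For early deaths and early permanent stops, this misplacement runs only from Q2W to Q4W.

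Safety is a co-primary objective, and Protocol 4.3.3 gives finding the most effective and safe cemiplimab dose as the reason for testing two regimens. Early fatal and treatment-ending events are central to that comparison, and the rule attributes them to the less intensive schedule.

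**Working it through.** The plan states no figure on this point, so the check applies the rule to dosing patterns and then counts.

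**Step 1. The rule applied** (SAP 2.3.2 with Protocol 8.3.1).

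| Allocated | Cemiplimab received | Safety column |
|---|---|---|
| Q2W | C1D1, then death or permanent stop | Q4W |
| Q2W | Day 1 doses only, every Day 15 omitted | Q4W |
| Q2W | C1D15 omitted, a later Day 15 dose given | Q2W |
| Q4W | C1D1, then death or permanent stop | Q4W |
| Q4W | Day 1 doses plus one isolated Day 15 dose | Q2W |

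Rows 1 and 4 fall together, so Q4W collects these events from both allocated arms and Q2W has none by construction.

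**Step 2. Formula.** Arms of 35 (SAP 1.1). Let d be the true events per arm, k the Q2W-allocated patients moved, and j those of the k with the event. The table then shows Q2W (d − j)/(35 − k) and Q4W (d + j)/(35 + k). All values of d, k and j are assumed.

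**Step 3. Rare early events, k = j = 1, equal true risk.**

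| d | True, each arm | Q2W shown | Q4W shown | Gap (points) |
|---|---|---|---|---|
| 1 | 1/35 = 2.9% | 0/34 = 0.0% | 2/36 = 5.6% | −5.6 |
| 2 | 2/35 = 5.7% | 1/34 = 2.9% | 3/36 = 8.3% | −5.4 |
| 3 | 3/35 = 8.6% | 2/34 = 5.9% | 4/36 = 11.1% | −5.2 |
| 4 | 4/35 = 11.4% | 3/34 = 8.8% | 5/36 = 13.9% | −5.1 |

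If only Q2W had one such event (1/35 against 0/35), the table would show 0/34 against 1/36 = 2.8%: the event appears in the wrong arm.

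**Step 4. Common events, d = 18, k = 1.** If the moved patient has the event: 17/34 = 50.0% against 19/36 = 52.8%, gap −2.8. If not: 18/34 = 52.9% against 18/36 = 50.0%, gap +2.9. If moved patients share the arm's rate, the average gap is 0.

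**Step 5. How often.** Only the cemiplimab-reaction route has data. In Study 1423 (Protocol 4.2.2.1), 5 of 353 patients (1.4%) had such reactions, and "all were non-serious and Grade 2 except 1 Grade 1 event". With 0/353 above Grade 2, the one-sided 95% upper bound is 1 − 0.05^(1/353) = 0.85%, and 35 × 0.00845 = 0.3 patients. That study had no haematologic malignancies. No rate is given for the other routes. At assumed totals of 2%, 5% or 10%, the average number moved is 35 × 0.02 = 0.7, 35 × 0.05 = 1.75 or 35 × 0.10 = 3.5.

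**The case against.** The strongest reply is that the effect may be trivial and the cases can be found elsewhere.

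- **Size.** Every count is assumed. In the lead example the shift is one patient. The standard error of a difference between two true rates of 2/35 is √(2 × (2/35)(33/35)/35), about 5.5 points, so the gap is about one standard error in a comparison that SAP 2.4 makes descriptive. This stands as a limit on size, but the shift is a systematic misplacement and not chance.
- **Discontinuation tables.** SAP 2.4.5.2 replaces them with listings when 5 or fewer patients discontinue for a TEAE, without saying whether that count is per arm. In a low-count trial those tables may not exist. This stands, and leaves the death table as the main place of harm.
- **Other outputs.** OS and PFS are analysed by allocated arm (SAP 2.3.1, 2.4.4). The randomised-population response listing gives the reason for discontinuation, and a swimmer plot shows time on treatment (SAP 2.4.4.2). The death listing gives cause and relationship (SAP 2.4.5.3). The cases remain identifiable, but the arm-level percentages stay wrong.
- **A tie-break is needed.** One Day 1 dose fits either schedule, and the SAP's choice is pre-specified. True, but as-treated analysis does not require this choice, and the allocated schedule breaks the tie without using outcome.

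A reader might go further and infer that the rule flatters Q2W across all safety tables. Step 4 does not support that: for common events the distortion can go either way. Nor does omitting C1D15 alone move anyone, since a later Day 15 dose restores Q2W. Nor does the SAP 2.1.3.1 convention, "BOR will be NE for patients who received at most 2 isatuximab administrations", show that early stops are expected in Q2W; it is an efficacy rule for every arm.

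**Conclusion.** The concern holds as to mechanism. Given a known Day 1 cemiplimab dose, the Q2W safety column can contain no death and no permanent cemiplimab stop before a Day 15 dose, whatever happens in the trial. That follows from the text alone.

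The size is not established. It rests on an assumed number of moved patients: one moved patient carrying a rare event gives a false gap of about 5 points in arms of 35, and none moved gives no gap. It would be wrong to conclude that the Q2W results will be materially misleading, or that early deaths are concealed. The affected outputs are the arm-level safety tables, chiefly deaths within 60 days and, when more than 5 patients discontinue for a TEAE, the discontinuation tables. ITT efficacy is unaffected, and this Q2W/Q4W rule does not alter pooled combination against control. The rule should be corrected because it gives wrong percentages when followed and is cheap to change.

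**What to change.** In SAP 2.3.2:

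- Keep the split between any cemiplimab (combination) and isatuximab only (control).
- Analyse cemiplimab-treated patients randomised to a combination arm under their IRT-allocated schedule. Early stopping, death, dose omission and protocol interval extension do not reclassify.
- Reclassify only if the irregularities documented under SAP 2.2.1 show that the other arm's schedule was given in error throughout treatment. An isolated Day 15 dose does not reclassify.
- For control-allocated patients given cemiplimab, keep the present Day 15 rule.
- List every patient whose safety arm differs from the randomised arm, with the reason. Also list patients kept in the allocated arm after part-treatment on the wrong schedule.

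A threshold on the share of cycles given wrongly should be avoided, because it again depends on time on treatment. Take a Q4W patient given Day 15 doses in error from Cycle 2. The share is 1/2 if treatment ends after Cycle 2 and 2/3 after Cycle 3, so a more-than-half rule would place the same error in different arms.

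The cost is SAP wording, one derivation and one listing, with no new data. The downside is that a patient on the wrong schedule for only part of treatment stays in the allocated arm, which the listing discloses.
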